### 6.1.12. Thermal Imaging

Evaluation of the thermal effect in the injected area compared to the contra-lateral non-injected area will be conducted at screening Day 1 (performed 28 through 7 days prior to baseline). Additional thermal imaging will be performed at clinic admission visit (Day -1), the day following drug injection ( $24h \pm 2h$  following drug injection) and on study visits Day 7, 14, 21, 28, and 56.

For the 3rd and 4th cohort (or in the 2nd cohort if 2 subjects experience intolerable side effects in the 3rd cohort) additional thermal imaging will be conducted every 28 days for an additional maximum period of 5 months.

Thermal imaging is non-invasive, non-radiating device that passively measures the emitting infra-red radiation of body surface with a sensitive ( $\pm$  0.1 °C) Infra-Red thermal camera (FLIR A310, ISO 9001-2008 Certified). Thermal imaging will include: a view of the injected area and the contra-lateral non-injected area – at a distance of 1 meter and in a horizontal line from the umbilicus. Thermal imaging will be performed in a room of 25  $\pm$  1 °C to reduce environmental influences on temperature reading according to a detailed written manual.

### 6.1.13. Fat Tissue Imaging: Magnetic Resonance Imaging (MRI)

Evaluation of Magnetic Resonance Imaging (MRI) in all cohorts will be conducted in eligible subjects after 2-hour fast at screening Day 2 (performed 14 through 2 days prior to baseline) and on Day 28.

For the 2nd cohort an additional MRI scan will be performed on Day 56.

For the 3rd and 4th cohort (and for the 2nd cohort if subjects experience intolerable side effects in the 3rd cohort) additional MRI scans will be performed every 28 days for an additional maximum period of 5 months

MRI scans of the abdomen will be performed using a 1.5 Tesla machine (General Electric -Signa or Siemens) using a body coil. Subjects will be examined after 2-hour fast in the supine position with arms positioned parallel along the lateral sides of the body. A breath-hold technique will be used to avoid motion artifacts when chest and abdomen are scanned. MRI scans demonstrating fat in the different compartments will be assessed using a MATLAB-based program. Fat tissues of specific anatomical landmarks will be quantified. In order to calculate the fat mass, 16 consecutive slices of 5mm width will be used: eight above the umbilicus and eight under the umbilicus (Figure 1). The scanner will utilize a 3D modified DIXON (mDIXON) imaging technique without gaps (5mm thickness and spacing of 5mm), fast-lowangle shot (FLASH) sequence with a multi-echo two-excitation pulse sequence for phasesensitive encoding of fat and water signals (TR,3.6ms; TE1,1.19ms; TE2,2.3ms; FOV 520×440×80mm; 2×1.4×1mm voxel size). Sixteen images of the phantoms will be generated, including in-phase, out-phase, fat and water phase. Images should be saved in a DICOM format with the information of date, subject's screening number and orientation (Left/Right) to be transferred by the Sponsor's request for analysis. MRI will be performed according to a detailed written manual.

[figure not shown]

[figure not shown]
Figure 1: MRI: Distribution of 16 Consecutive Slices

#### **6.1.14. Biopsy**

On Day 56 (following MRI), in 3 randomly selected subjects of the 3rd cohort (or the 2nd if 2 subjects experience intolerable side effects in the 3rd cohort) an abdominal SC adipose tissue biopsy will be taken from the injected side. The Sponsor or designee will select 3 subjects to go under a biopsy: two subjects who will be demonstrating clear thermogenesis (assuming an active) and one subject who will not demonstrate thermogenesis (assuming a control). Before biopsy the Sponsor representative who is un-blinded to the study will confirm that the selected subjects are indeed 2 RZL-012 treated and 1 vehicle treated. Subjects will be followed 7 days post biopsy and will terminate their study participation.

After local anesthesia, an elliptical excision biopsy will be conducted by a trained medical professional 10 cm lateral to the umbilicus lateral wall (Figure 2). A sample of fat tissue (a biopsy of an ellipse of 15-20 mm deep and 4.5-6 cm long, Figure 2) will be taken from the incision. For optimal cosmetic results the incision will be made on a slant following Langer's lines. The incision will be stitched appropriately and the wound will be covered with a bandage or sterile dressing. The sample will be divided in two. One half will be placed in a vial filled with a fixation solution (formaldehyde). After 24h ± 2h, the fixation solution should be exchanged to ethanol 80% and further processed for histological analysis. Each vial and lid will be labeled with: subject's name, subject's identification number and biopsy site. The other half of the biopsy will be embedded in a labeled cryomold with Optimum Cutting Temperature (OCT) compound and flesh frozen using a cryostat or liquid nitrogen. Each sample will be labeled with: subject's name, subject's identification number and biopsy site. Biopsies will be sent to the sponsor in an adequate manner and evaluated by a certified pathologist. Biopsies will be stained for hematoxylin and eosin stain (H&E) and further evaluated for BAT and other markers and morphometry.

Figure 2: Biopsy Site and Dimensions

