# PROTOCOL SYNOPSIS

Protocol Number	RZL-012-P2aUS-001.2
Protocol Title	A Double Blind, Randomized, Placebo Controlled, Dose Escalation Phase 2a Clinical Trial for the Evaluation of Safety and Thermogenesis-induction of RZL-012 in Overweight and Obese Volunteers
Study Phase	Phase 2a
Study Drug	RZL-012
Study Objectives	Primary objective : Evaluation of the overall safety and preliminary efficacy of RZL-012 after injection into the subcutaneous fat.
	Secondary objective: Determination of RZL-012 pharmacodynamics and pharmacokinetics. Evaluation of the existence of a thermogenic effect and the extent, duration and tissue associated changes of the thermogenic response to RZL-012, via minimal invasive means (injected-site thermogenesis imaging, Magnetic Resonance Imaging (MRI) and biopsy) after subcutaneous injection into fatty tissue below the skin.
Sample Size	32 subjects
Study Design	This is a consecutive 4 cohort, dose escalation placebo-controlled clinical trial in overweight and obese subjects. All cohorts will be comprised of 6 active (RZL-012) and 2 placebo subjects.
	Within each cohort, dosing of the first 3 subjects will progress consecutively from one individual to the other at 7-day intervals. For additional precaution, the first 3 subjects will be forced randomized into 2 active and 1 control. This study design will allow the physicians to monitor safety in a two subjects at each dose, nevertheless the blindness will remain intact. The remaining subjects in a cohort will be randomized to either active treatment or placebo in a ratio determined by the number of subjects targeted for each cohort. Dosing of the next subjects will be in couples and the last subjects will be in a triplet.
	If intolerable side effects in a cohort occurs, dosing will progress subject by subject, rather than in couples or triplet.
	The trial will proceed within a cohort and from one cohort to the next as long as no more than one subject experiences intolerable side effects in the lower-dose cohort, and based on the decision made by a Data and Safety Monitoring Board (DSMB). The decision to proceed to the next cohort will be made after reviewing all safety data collected by Day 14 within $2 \pm 1d$ of the last dosed subject in each cohort. If two (2) intolerable side effects are observed in any dose cohort, further treatment at that dose will be stopped and only tolerable doses used for further subjects.

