#### Follow-up visits (Day 29-168):

Subjects of the 1st and 2nd cohorts:

- On visit Day 56 will come after overnight fast (10-12hr fast) for the glucose, insulin, lipid profile tests and FFA levels. Subjects will be followed up for anthropometric measurements, thermal imaging and adverse events. An MRI scan will be conducted on Day 56 in subjects of the 2nd cohort.
- Will continue to be followed for safety every 28 days till Day 112. If Draize-score is 0 for edema and erythema by visit Day 56 then subjects will be followed by phone call for AE.

Subjects of the 3rd and 4th cohorts (or treated with the highest dose achieved):

- Will be followed up for anthropometric measurements (e.g., BMI, WHR) every 28 days as long as the thermogenic effect is apparent and for a period that will not exceed 6 months from the beginning of treatment.
- Subjects will record their weight following 10-12hr fast (overnight) fast and at bedtime once a week when not visiting the site, in a diary. Diaries will be checked and data will be captured in the CRFs.
- In addition, evaluation of the injected area and the contra-lateral side will be performed by Draize score, photographs and thermal imaging
- Subjects will come fasting (10-12hr fast) for the glucose, insulin, lipid profile tests and FFA levels.
- MRI of 16 slices that includes the injected site (SAT evaluation). MRI will be conducted on Day 28 days and every 28 days for a period that will not exceed 6 months from the beginning of treatment in the 3rd and 4th cohorts.
- On Day 56 (following MRI), in 3 randomly selected subjects treated with the 3rd cohort (2 RZL-012 treated that show a sustained thermogenic effect by thermal camera imaging and one subject treated with vehicle with no thermogenic effect), an abdominal subcutaneous (SC) adipose tissue biopsy will be taken from the injected side. The biopsy site will be anesthetized with 1% lidocaine and will be performed by a trained medical professional. The sample (an elliptical excision of 15-20mm deep and 4.5-6cm long) will be placed in a vial filled with a fixation solution (formaldehyde). After 24h ± 2h, the fixation solution should be exchanged to ethanol 80% and further processed for histological analysis. Biopsies will be stained for hematoxylin and eosin (H&E) and further evaluated for BAT

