#### 3.3. DOSING

#### 3.3.1. Dosing Regimen

The dosing regimen will be a single dose treatment injection of RZL-012 in multiple sites.

The first 6 subjects randomly assigned to the RZL-012 treatment group (cohort 1) will initiate at the dose of 40 mg RZL-012 (approximately 1/6.25th the NOAEL as determined in the GLP toxicology study) and 2 more subjects will be given placebo (vehicle).

If no more than 1 subject experiences intolerable side effects within the 1st cohort, 14 days following the injection of the last dosed subject, an additional 6 subjects will receive a dose of 80 mg RZL-012 (approximately 1/3.125th of the NOAEL) and 2 more subjects will be given placebo (vehicle).

If no more than 1 subject experiences intolerable side effects within the 2nd cohort, 14 days following the injection of the last dosed subject, an additional 6 subjects will receive a dose of 120 mg RZL-012 (approximately1/2.34th of the NOAEL) and 2 more subjects will be given placebo (vehicle).

If no more than 1 subject experiences intolerable side effects within the 3rd cohort, 14 days following the injection of the last dosed subject, according to schedule an additional cohort of 6 volunteers, as above, will receive 180 mg RZL-012 (1/1.39 of the NOAEL). Additional 2 subjects in the cohort will serve as control and will be injected placebo (vehicle).

Dosing of the first 3 subjects in each cohort will progress consecutively from one individual to the other at 7-day intervals. For additional precaution, the first 3 subjects will be forced randomization with 2 active and 1 control. This study design will allow the physicians to monitor safety in a single subject at each dose; nevertheless, the blindness will remain intact.

The next subjects in the cohort will be randomized to either active treatment or placebo in a ratio determined by the number of subjects targeted for each cohort. Dosing of the next subjects will be in couples and the last subjects will be in a triplet.

If 1 subject had already experienced intolerable side effects in a cohort, then enrollment will progress consecutively from one individual to the other at 7-day intervals until that cohort is complete.

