# 6. RELATED DOCUMENTS (OPTIONAL)

- 6.1 Study Protocol: RZL-012-P2aUS-001.4\_track changes 04 Mrch 2018
- 6.2 Randomization plan: RZL-012-P2aUS random plan final version 1.0 01-08-2017.pdf

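### Confirming the biopsied cohort 3 trio as two active and one vehicle, alongside the stated 2+1 first block, lets an informed reader deduce the arms of about two of the five non-biopsied subjects

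*Protocol*

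**What the plan says.** **Allocation.** The Protocol Synopsis states: "All cohorts will be comprised of 6 active (RZL-012) and 2 placebo subjects". Within a cohort, "the first 3 subjects will be forced randomized into 2 active and 1 control"; section 3.3.1 repeats this ("the first 3 subjects will be forced randomization with 2 active and 1 control"), as does SAP 5.4.3. The remaining subjects are randomised "in a ratio determined by the number of subjects targeted for each cohort". The synopsis and section 3.3.1 both say that blinding survives this arrangement.

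**Biopsy.** Protocol 6.1.14 says the biopsy is done "in 3 randomly selected subjects" of cohort 3. The same section then has the Sponsor or its designee choose two subjects with clear thermogenesis, presumed active, and one without, presumed control. Before the biopsy, an unblinded Sponsor representative "will confirm that the selected subjects are indeed 2 RZL-012 treated and 1 vehicle treated". The synopsis (Follow-up visits) ties arm to response: two RZL-012 subjects with a sustained effect and "one subject treated with vehicle with no thermogenic effect".

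**Afterwards.** Biopsied subjects are followed for 7 days and then leave. The other cohort 3 subjects may be followed to Day 168.

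**Access.** Neither document says who may learn the result of the confirmation. The SAP (section 6) cites a separate document, "Randomization plan: RZL-012-P2aUS random plan final version 1.0", so a restricted place for allocation detail already exists.

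**The concern.** Two pieces of information are harmless apart and informative together. The block structure alone identifies nobody. The biopsy confirmation alone identifies only the three biopsied subjects. A reader with both can work outwards from the trio to subjects who were never biopsied, because each block holds exactly one control.

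It makes little difference that the documents do not say the confirmation is sent to the site. The protocol makes the 2-and-1 composition a condition of the biopsy, so the biopsy going ahead conveys the answer.

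At stake is the blind in the continuing cohort 3 subjects. Causality is the investigator's medical judgement (Protocol 9.3), an event counts as intolerable only if judged possibly or probably related (3.3.2), and Draize scores are read by eye (6.1.10). Duration of the thermogenic effect is the first secondary endpoint (4.2).

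**Working it through.** The documents give no figure for deducible assignments. Their own totals reproduce: 4 × (6 + 2) = 32 subjects, with 4 × 6 = 24 active and 4 × 2 = 8 placebo.

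**Inputs**
- Cohort of 8: 6 active, 2 placebo (Synopsis; 3.1).
- First three: 2 active, 1 control (Synopsis; 3.3.1; SAP 5.4.3).
- Last five, by subtraction: 6 − 2 = 4 active and 2 − 1 = 1 control. The protocol does not print this split.
- Trio: 2 active and 1 vehicle, with the vehicle subject known to be the one without thermogenesis (6.1.14; Synopsis).

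**Assumptions.** The reader knows the dosing order, there are no replacements, and every trio of two actives and one control is equally likely.

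**Enumeration.** There are 3 × 5 = 15 allocations. Each has C(6,2) × 2 = 15 × 2 = 30 possible trios, giving 450 cases. An arm counts as known if it is the same in every allocation consistent with the blocks and the trio. Let j be the number of biopsied actives who come from the first block.

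| j | Active pairs (of 15) | Arms known, vehicle subject in first three | Arms known, vehicle subject in last five |
|---|---|---|---|
| 0 | C(4,2) = 6 | 5 | 5 |
| 1 | 2 × 4 = 8 | 4 | 6 |
| 2 | 1 | 3 | 8 |

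- Vehicle subject in first three: (6×5 + 8×4 + 1×3)/15 = 65/15 = 4.33.
- Vehicle subject in last five: (6×5 + 8×6 + 1×8)/15 = 86/15 = 5.73.
- Overall: (65 + 86)/30 = 151/30 = 5.03 of 8.
- Non-biopsied subjects revealed: 5.03 − 3 = 2.03 of 5 (1.33 or 2.73 by block).

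Over the 450 cases, 3, 4, 5, 6 and 8 arms are known in 15, 120, 180, 120 and 15 cases. At least one non-biopsied subject is revealed in 450 − 15 = 435 (97%).

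**Which arm is revealed.** The second vehicle subject is identified only where all 8 arms are known: 15/450 = 3.3%. In the other 435 cases every extra subject deduced is active. With the 6/2 total and the trio known but no block split, each of the remaining five already has a 4/5 = 80% chance of being active. The block split mostly moves about two subjects from 80% to 100%.

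**What drives the result**

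| Reader knows | Mean arms known |
|---|---|
| Blocks, trio, and which one is the vehicle subject | 5.03 |
| Trio and which one is the vehicle subject, no blocks | 3 |
| Blocks and trio, but not which one is the vehicle subject | 0.4 |
| Blocks only, no confirmation | 0 |

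**Timing.** If one intolerable effect has occurred in a cohort, dosing continues singly at 7-day intervals (3.3.1). In the extreme case the eighth subject is dosed 7 × 7 = 49 days after the first, and is at Day 56 − 49 = 7 when the first reaches Day 56. A confirmation made then would come before that subject's Day 28 reading. Under faster dosing the overlap is smaller.

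**The case against.** The strongest reply is that little is lost. It has several parts.

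- **Three of the 5.03 are the biopsied subjects, who leave a week later.** This stands. The continuing exposure is about two subjects, nearly always active ones, and those with thermogenesis were already presumed active.
- **The key endpoints come first.** Escalation rests on Day 14 data (3.3.1) and thermogenesis is judged by Day 28 (6.1.17.1.2). This stands for subjects already past those visits when the trio is confirmed, but not necessarily for later-dosed ones. Temperature and fat mass come from a camera and a MATLAB-based program (6.1.12, 6.1.13), which limits observer bias.
- **Follow-up to Day 168 is not assured for all five.** The synopsis (Follow-up visits, Study Duration) and 6.1.17.2.1 make parts of it depend on thermogenesis; the MRI item and the schedule tables do not. This stands in part.
- **The deduction needs extra knowledge.** This stands. A protocol alone is not enough: the reader must know which of the trio lacked thermogenesis. The Sponsor's selector does, and so would site staff who see the thermal images.
- **Replacements in cohort 3 (5.4) can break the block pattern.** This stands, and the figures assume none.
- **The blind may already be open.** Protocol 6.2.2 speaks of revealing assignment just before treatment, which could be read as unblinding the Investigator at Day 0. But that sentence describes how the Investigator is masked, and only the pharmacist is named as unmasked. It needs its own clarification and does not dispose of this point.

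Thermogenesis as a natural clue does not answer the concern. The plan itself treats it as a presumption that needs checking, and the check turns the presumption into certainty.

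**Conclusion.** The point holds at modest size. As written, the plan lets an informed reader know the biopsied trio's arms for certain and deduce, on average, about 2 of the 5 non-biopsied cohort 3 subjects. This does not fit the statement that blinding is preserved. The figures rest on knowing the dosing order and which of the trio was the vehicle subject, on equally likely trios, and on no replacements. If the vehicle subject is more likely to come from one block than the other, the mean still lies between 4.33 and 5.73.

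A reader might infer more than the documents support:
- **That five of eight continuing subjects are unblinded.** Three of the five have left, and the second vehicle subject is identified in only 3.3% of cases.
- **That the primary efficacy result is compromised.** It is read by Day 28, and only staggered dosing could bring a confirmation ahead of it for some subjects.
- **That home weights are biased.** Nothing gives subjects the block structure, the dosing order or other subjects' thermal results.
- **That a wrong first selection leaks further arms.** No correction procedure is described, so this is only a possibility.

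The outcomes exposed are AE causality, Draize scoring and the conduct of continued follow-up, in a trial whose analysis is mainly descriptive. The change is worth making because it is cheap.

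**What to change.** 1. In Protocol 6.1.14, replace confirmation with silent selection. The Sponsor or designee supplies a masked list of cohort 3 subjects with and without thermogenesis. The already unblinded representative chooses the three and returns subject numbers only, with no confirmation or correction.
2. Move the trio's arm composition out of 6.1.14 and the synopsis (Follow-up visits) into an unblinded biopsy instruction. It should also say what the representative does if the list cannot supply the intended trio.
3. Reconcile the description of the three as random with selection on thermogenesis, for example by stating that the representative draws at random among listed subjects who qualify.

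The 2+1 first-block rule can stay in the protocol and SAP. It is a stated safety precaution, the Sponsor knows it anyway, and without the confirmation it reveals no individual arm with certainty: the mean falls from 5.03 to 0 for a reader who does not know the trio's composition.

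The cost is a wording change and one short restricted document. The benefit is partial where staff have already read the present text, since they may still guess the trio's composition.

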#### 6.1.15. Pharmacokinetics

Testing of RZL-012 Pharmacokinetics will be conducted at the baseline visit till the following day (Day 0-1). Subjects will stay overnight in the study center. Blood samples (10 mL blood per sample in K2EDTA vials, 100 mL/subject/24h) will be taken after injection at the given time points: 0, 30, 60 min, 2h, 3h, 4h, 6h, 8h, 12h, 16h,24h, 30h in subjects from all cohorts. Whole blood samples (10 mL x12 time points) will be stored on an ice block or wet ice until centrifuged. Samples will be placed in the centrifuge and spin cycle started within 60 minutes of collection. Samples will be centrifuged at 1200 g in 4 °C for 10 minutes. Plasma will be removed and placed in aliquots (4 aliquots of 1 mL each) within 20 minutes of centrifugation and flash frozen on dry ice. Processed samples will be placed in frozen (-60 to -90 °C) storage. Determination of RZL-012 in K2EDTA human plasma a validated method of Liquid Chromatography-Tandem Mass Spectrometry will be conducted and analyzed by Analyst Research Laboratories Ltd. Samples (2 aliquots/subject/time point) will be sent to Analyst frozen on dry ice and 2 aliquots will be retained for possible future analysis.

#### 6.1.16. Adverse Events

The information obtained during weekly subjects questioning, review of subject's compliance record, physical examinations, vital signs measurements, blood testing, and by any other means will be evaluated in light of baseline medical data and thus provide the basis for adverse events identification and grading.

The trial will proceed within a cohort and from one cohort to the next as long as no more than one subject experiences intolerable side effects and based on the decision made by a DSMB. Proceeding from one cohort to the next will be based on the decision made after reviewing all safety data collected by Day 14 within  $2 \pm 1d$  of the last dosed subject in each cohort. The DSMB will be comprised of two independent MDs expert in early phase clinical trials.

The adverse events reported during the trial will be graded (see Section 9), documented, and assessed in light of their clinical significance and relation to investigational product. In addition, the following information regarding the AE must be obtained: AE description, start date, end date (if applicable) or ongoing, severity, seriousness, relationship to study drug, outcome (e.g., resolved / unresolved), and action taken (e.g., concomitant medication). The sponsor or the sponsor representative will provide information regarding SAE expectedness based on data included in the IB. Adverse event monitoring will be conducted throughout subject's participation up to 28 days after injection. For the 1st and 2nd cohort subjects will be additionally followed for AE at visit Day 56. If Draize score is 0 for erythema and edema, subjects of these cohorts and subjects of the 3rd and 4ths who terminate the study before visit Day 112, will be followed at Day 84 and Day 112 by phone-call questioning. For the 3rd and 4th cohort (or the highest dose achieved) adverse events will be recorded after Day 28 every 28 days if subject did not terminate participation in the study.

